#### *6.1.4.1 Inclusion and exclusion criteria*

Inclusion: Participants will be women aged over 70 years, registered with a participating GP practice.

Exclusion: Inability to consent or participate due to a significant physical or mental disorder or disability, insufficient competence in English language or other language difficulty. The decision as to who should be excluded under these criteria will rest with the GP practice, who are best placed to make this decision.

#### *6.1.5 Analysis*

*6.1.5.1 Primary research question: Does the Promoting Early Presentation (PEP) intervention increase breast cancer awareness in older women (over 70 years) when used in a general practice setting?*

The validated Breast Cancer Awareness Measure will be used to categorise participants as aware or not aware. A McNemar's test for paired proportions will be used to compare the proportions of aware to not aware at one month and twelve months after the delivery of the intervention.

*6.1.5.2 Secondary research question: Which, if any, demographic factors are associated with successful PEP intervention in primary care settings?*

A logistic regression model will be built using the binary Breast Cancer Awareness Measure outcomes as the outcome variable (dependant variable) and the demographic factors collected as the predictors (independent variables). If the predictors are found to be highly correlated, a principal component analysis may be undertaken to identify mutually orthogonal components which typify the underlying dimensions of the demographic variables.

6.1.5.3 *Secondary research question: What are the barriers to successful outcomes from a service user perspective?*

All telephone interviews will be fully transcribed and analysed thematically. The research team are keen that the voices of participants should be prioritised in any outputs from the study. To enable this, anonymised direct quotes will be used wherever possible, with consent, in project outputs.

6.1.6 *Ethical issues*

The research project will be subject to scrutiny by an NHS REC committee. The underlying principle of the data collection is that of protection; acknowledging that those working to collect data as part of the study are responsible for the well-being of participants. Ethical considerations will be constantly re-assessed by researchers trained to follow strict ethical codes of practice. Should further issues to those identified below arise, these will be discussed with the stakeholders of the study and amongst the research team at the lead institution (University of Northampton). Appropriate strategies will then be developed and any changes in protocol or practice will be referred for approval as per NHS REC guidelines.

[figure not shown]
The following issues specific to this study have been identified and procedures planned for to mitigate them. Where reference is made to 'participants' this relates to patients to whom the PEP intervention has been delivered.

- Consent: All participants of the research will be fully informed of the aim and emphasis of the study and given time (a minimum of 24 hours) to reflect on this before being given the opportunity to opt in (via completion of a research questionnaire applying implied consent) or out of the research project. Patients will be invited to receive the intervention via their GP practice (all practices participating will be part of the Primary Care Research Network). Potential participants will be informed of their right not to participate via information distributed with the questionnaire. This information also states that, should they choose not to participate, this will not impact on the treatment or advice that they receive from their GP surgery.

- Anonymity and confidentiality: All participants of the research will be informed as to how the data will be stored and used and assured of their anonymity in subsequent publications of the findings.
- Data storage and transfer: No personal contact information will be stored with data collected as part of the completion of the project and research questionnaires will not be linked to patient medical records. Each participant will have a unique identifying number in order to link the data collected from them in the three Breast Cancer Awareness Measures and the demographic questionnaire. However, only the practices, who will be responsible for contacting the participants, will have the key to link these identifiers with names and addresses. This key will be stored securely, and separately from the medical records. The University research team will therefore not have access to the personal identifiable information of participants, except for those patients who opt to form part of the telephone interview sample. For this sample, the University team will keep the contact details of those who volunteer this information, together with their unique identifier, separate from their data which will be stored with only the unique identifier. Research questionnaires will be securely transferred to the University team and the hardcopies of these will be stored in a locked cabinet. All data collected as part of the project shall be stored securely according to the guidelines set by the Data Protection Act (1998) and the Freedom of Information Act (2000). All electronic information will be filtered with anti-virus software. All data collected as part of the research will be destroyed 5 years after the conclusion of the project.
- Feedback: The results of the study will be made available to the general public via the normal public communications employed by NHS Northamptonshire.
- Additional issues: It is possible that participants may become anxious as a result of their breast cancer awareness intervention, although this project has been carefully designed to minimise the likelihood of this and interventions will be delivered by qualified practice nurses. The practice nurses are ideally placed to reassure participants and, should it be necessary, can refer them to their GP for further discussions.

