### 6.1.2 Methods

The efficacy of this intervention in a population of older women attending for mammography screening has already been established in a randomised control trial. This study will investigate whether the intervention is also effective when implemented in a more general primary care setting, and will use observational methods to compare participants' breast awareness before and after the delivery of the PEP intervention (both in the short and long-term).

Participants (for sampling and recruitment methods see 6.1.3 and 6.1.4) will be asked to complete a **validated measure of breast cancer awareness** (the Breast Cancer Awareness Measure) on three occasions: during recruitment to the project, again one month after they have had the educational intervention and 12 months after the intervention. Additionally, participants will be asked to complete a **short questionnaire** relating to demographic and socio-economic information. This will enable the research team

to collate information about those factors previously identified as being associated with reduced use of health services:

- Age
- Postcode (for Indices of Multiple Deprivation analysis)
- Ethnicity
- Details of first/second language
- Formal education level
- Disability
- Transport provision
- GP surgery (for calculation of distance between residential location and surgery)

The intervention training will be delivered to each participating practice nurse by staff of the University of Northampton and NHS Northamptonshire who have been trained to do so by the Kings College team (for details, see section 4). The trained practice nurses will then deliver the intervention as part of this project.

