### *6.1.3 Sample size*

The primary research question of the proposed study will test the null hypothesis that there is no relationship between the validated Breast Awareness scale outcome (not aware vs. aware) and the time at which the outcome was measured (before vs. 12 months after). This will be tested by the McNemar test for paired proportions. The criterion for significance (alpha) has been set at 0.05 (2-tailed).

The power analysis is based on the following population effect size, derived from previous research: in 90.0% of pairs, both cases will be classified as not aware and in another 4.0%

both cases will be classified as aware. These cases contribute no information to the hypothesis test.

A discrepancy between the two members of a pair is expected in the balance of the population: 1.0% of all pairs will show an outcome of aware for the before case only, while 5.0% of all pairs will show an outcome of aware for the after case only. This effect was selected as the smallest effect that would be important to detect, in the sense that any smaller effect would not be of clinical or substantive significance. This effect size is reasonable, in the light of results from previous research in this field.

A proposed sample size of 250 (at 12 month follow-up) will have power of 80.7% to yield a statistically significant result. The attrition rate between baseline and immediately after the intervention will be low as the participants will bring their completed questionnaire to their booked appointment and complete the post-intervention questionnaire immediately after their appointment (estimated 5% drop-out). However, the drop-out rate to the 12-month follow-up is likely to be substantial and has been conservatively estimated at 50%. Hence 532 participants will need to be recruited for the intervention in order to ensure that 250 are available for analysis after 12 months.

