#### *6.1.4 Recruitment*

The participating GP practices will be recruited through the Primary Care Research Network (EM SY) and the participating practice staff will have undergone training in the conduct of research.

The study participants will be women over the age of 70 years. This is a group that are known to have lower breast cancer awareness, are more likely to delay presentation in breast cancer, and have worse outcomes than younger women. This age group is the focus of work being undertaken by the East Midlands Cancer Network. Currently women over the age of 70 years do not receive a routine invitation for NHS breast screening (this facility will be extended to women aged 71-73 by 2016). An estimated 18 GP practices, identified via the PCRN, will recruit approximately 30 participants each to the study (to a total of 532 participants). The recruitment of the participants for the study will be done via the GP practices, who will identify those eligible for inclusion, send out invitation letters and the pre-intervention questionnaire. The GP practices will arrange the appointments and deliver the intervention. The post-intervention questionnaires will be sent out by the practices. All

completed questionnaires, linked with a unique identifier, will be returned by the participants to their GP practice, who will then forward them to the CHWR for analysis.

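### The primary McNemar test and its 80.7% power treat 250 women from about 18 practices as independent pairs; if the before-after change varies by practice, p-values are too small and power is overstated

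*Protocol*

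**What the plan says.** The protocol fixes the primary test in two places. Section 6.1.3 sets the null hypothesis of no relationship between awareness and time (before against 12 months after) and adds: "This will be tested by the McNemar test for paired proportions". Section 6.1.5.1 repeats the test for one and twelve months: "A McNemar's test for paired proportions will be used to compare the proportions of aware to not aware".

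Section 6.1.3 bases power on pair proportions. It expects 90% of pairs to be not aware at both times and 4% to be aware at both. For the discordant pairs it states: "1.0% of all pairs will show an outcome of aware for the before case only, while 5.0% of all pairs will show an outcome"; the second figure is for women who are aware only at the later time. It concludes: "A proposed sample size of 250 (at 12 month follow-up) will have power of 80.7% to yield a statistically significant result". Alpha is 0.05, two-sided.

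On structure, section 6.1.4 says: "An estimated 18 GP practices, identified via the PCRN, will recruit approximately 30 participants each to the study (to a total of 532 participants"). The practices also identify and invite the women, arrange the appointments, deliver the intervention and send the later questionnaires. Section 6.1.2 says: "The trained practice nurses will then deliver the intervention as part of this project". Section 4 plans two training courses of up to 12 nurses each, so at most 24 nurses.

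Section 6.1.2 lists GP surgery among the items collected, but only to calculate distance. The protocol mentions no ICC, design effect, practice term or cluster-robust variance.

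**The concern.** McNemar's test compares the number of women who become aware with the number who cease to be aware, and treats each woman as an independent observation. Here one nurse, or a few, treats all the women in a practice through a one-to-one conversation, and the same practice handles invitation and follow-up. Nurse skill, fidelity to the script and practice procedures can all affect how much awareness changes.

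Each woman is her own control, so differences between practices in the level of awareness largely cancel. Differences in change do not. If they exist, the variance of the net change is larger than McNemar assumes. The p-value is then too small, and 250 women carry less information than 250 independent pairs.

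This matters because the study is an uncontrolled before-after comparison, and the primary p-value carries the statistical conclusion about whether the intervention works in general practice. Both the test and the power are fixed in the protocol, so this is not a detail awaiting a SAP.

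**Working it through.** **Inputs from the protocol.** Discordant pairs 5% and 1% (6% in total), 250 analysed, two-sided alpha 0.05, power 80.7% (section 6.1.3); 18 practices (section 6.1.4); at most 2 × 12 = 24 nurses (section 4).

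**Assumed, because the protocol gives none.** ICC of the within-woman change: 0.01, 0.02, 0.05.

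**Step 1: reproduce 80.7%.** Expected discordant pairs: 250 × 0.06 = 15. Arcsine effect size: h = 2·asin(√(5/6)) − 2·asin(√0.5) = 0.7297. Power = Φ(h·√15 − 1.96) = Φ(2.826 − 1.96) = 80.68%. This matches the stated figure with all 250 pairs independent, that is, a design effect of 1.

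**Step 2: apply a design effect.** Women per practice: m = 250/18 = 13.9. Design effect DE = 1 + (m − 1)·ICC; effective N = 250/DE; power = Φ(h·√(0.06 × effective N) − 1.96). The approximate true alpha of an unadjusted test is 2·[1 − Φ(1.96/√DE)].

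| ICC of change | DE | Effective N | Power, protocol's formula | Approximate true alpha |
|---|---|---|---|---|
| 0 | 1.00 | 250 | 80.7% | 5.0% |
| 0.01 | 1.13 | 221 | 75.8% | 6.5% |
| 0.02 | 1.26 | 199 | 71.2% | 8.1% |
| 0.05 | 1.64 | 152 | 59.6% | 12.6% |

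With the nurse as cluster (250/24 = 10.4 women each), DE is 1.09, 1.19 and 1.47, and power is 77.1%, 73.7% and 64.4%.

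**Step 3: type I error by simulation.** 18 practices of 13 or 14 women, 3% becoming aware and 3% ceasing to be aware on average, with change varying between practices; 20,000 runs.

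| ICC of change | Uncorrected McNemar | Exact McNemar |
|---|---|---|
| 0.01 | about 6% | about 3.5% |
| 0.02 | about 8% | about 5% |
| 0.05 | about 12% | 8-9% |

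Cluster-adjusted tests on the 18 practices held their size, at 4.1% to 5.1%.

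**Step 4: power of a cluster-adjusted test by simulation, at 5% and 1%.** About 71% at ICC 0, 63% at 0.02 and 52% at 0.05. The first value already lies below 80.7% with no clustering at all. The arcsine formula is optimistic: with 250 independent pairs, the two-sided power of the ordinary McNemar test is 69.3% in its exact form and 77.0% uncorrected. Clustering therefore accounts for the fall from 71% to 63% or 52%; the gap between 80.7% and 71% comes from the formula and the change of test.

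**The case against.** - **The inflation is conditional.** A reader might infer that the false-positive rate certainly exceeds 5%. The protocol does not support that. If no practice has any systematic change, McNemar keeps its size however much practices differ in level. The simulated null needs gains in some practices balanced by losses in others. This stands, and the conclusion is worded accordingly.
- **Delivery is standardised.** Section 4 describes a scripted contact of about six minutes with a booklet, taught by one training team. This limits variation between nurses but does not exclude it.
- **The upper ICC is large at these rates.** For a conversion rate of 3%, an ICC of 0.05 implies a between-practice SD of √(0.05 × 0.03 × 0.97) = 3.8 percentage points, more than the mean itself; 0.02 implies 2.4 points. The 0.05 row is best read as the unfavourable end of the range.
- **The exact test absorbs some of it.** Exact McNemar is conservative with about 15 discordant pairs and stays near 5% up to an ICC of about 0.02. The protocol does not say which version it means, and the exact test does not hold at 0.05.
- **A large effect would survive.** If 20% became aware and 1% ceased to be (an assumed case), z = (50 − 2.5)/√52.5 = 6.6, and 6.6/√1.64 is about 5.1. True, but the protocol powers the study for the smallest effect it regards as important, where the adjustment matters.
- **Few discordant pairs per practice.** With about 15 across 18 practices, a clustered test might seem fragile. The simulated size of 4.1% to 5.1% answers this.

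**Conclusion.** The point holds in conditional form. The fixed primary test and its 80.7% power assume 250 independent pairs, while the women are nested in about 18 practices. If the ICC of change lies between 0.01 and 0.05, power on the protocol's own formula is about 76% to 60%, and the type I error is about 6% to 12% for the uncorrected test or 3.5% to 8-9% for the exact one. These sizes rest on the assumed ICC and on equal numbers analysed per practice.

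Three stronger readings are not supported:

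- That the study's confidence intervals are too narrow. The protocol plans none for its own analysis; those in section 5 belong to the earlier randomised trial.
- That clustering alone takes power from 80.7% to 52%. About 10 points of that fall are present at ICC 0.
- That the secondary logistic regression is wrongly specified. Section 6.1.5.2 names no variance estimator, and practice-clustered errors there can be left to the SAP.

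**What to change.** In sections 6.1.3 and 6.1.5.1, replace the ordinary McNemar test with a cluster-adjusted paired test, with practice as the cluster. Any one of these would do, if named in advance:

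- a clustered McNemar test (Durkalski or Obuchowski type);
- GEE with practice as cluster and a small-sample variance correction for 18 clusters;
- a one-sample t test on the 18 practice-level net changes.

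In section 6.1.3, state that the ICC of change is unknown and give the power of the chosen test over an ICC of 0.01 to 0.05, with the ICC 0 value beside it so that the cost of clustering can be seen. Recruitment need not change. In section 6.1.2, add the analysis to the stated purposes of collecting GP surgery.

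The cost is protocol wording and minor programming on data already collected. The downside is a somewhat larger p-value and a stated power below 80.7%.

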## 6 Research project

### 6.1.1 Research questions

This project aims to investigate the effectiveness of the Kings College interventional programme when implemented in a general practice setting, delivered by practice nurses. If increased breast awareness is seen in this setting, it will potentially lead to a sustainable model of improving the early presentation of breast cancer symptoms in women aged over 70 years. This is a group that are known to have lower breast cancer awareness, are more likely to delay presentation in breast cancer, and have worse outcomes than younger women.

The primary research question for the study is therefore:

***Does the Promoting Early Presentation (PEP) intervention increase breast cancer awareness in older women (over 70 years) when used in a general practice setting?***

Secondary research questions:

- *Which, if any, demographic factors are associated with successful PEP intervention in primary care settings?*
- *What are the barriers to successful outcomes from a service user perspective?*

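### The primary analysis sentence in 6.1.5.1 names one month and twelve months but not baseline, and so does not match the before-versus-12-months test that 6.1.3 sizes

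*Protocol*

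**What the plan says.** The primary question (Protocol 6.1.1, repeated as the heading of 6.1.5.1) is: "Does the Promoting Early Presentation (PEP) intervention increase breast cancer awareness in older women (over 70 years) when used in a general practice setting". Awareness is measured three times (6.1.2): "during recruitment to the project, again one month after they have had the educational intervention and 12 months after the intervention".

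Three sections describe the comparison that should answer the question:

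- **6.1.2 Methods.** The study will "compare participants' breast awareness before and after the delivery of the PEP intervention (both in the short and long-term"). This is a before/after comparison over two horizons.
- **6.1.3 Sample size.** The null hypothesis is no relationship between awareness and "the time at which the outcome was measured (before vs. 12 months after"). The section adds "This will be tested by the McNemar test for paired proportions" and "The criterion for significance (alpha) has been set at 0.05 (2-tailed"). Its discordant cells are defined against baseline: "1.0% of all pairs will show an outcome of aware for the before case only", and 5.0% are aware afterwards only.
- **6.1.5.1 Analysis, primary question.** McNemar's test will be used to "compare the proportions of aware to not aware at one month and twelve months after the delivery of the intervention". The baseline measure does not appear, and the two follow-up times are not ranked.

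**The concern.** McNemar's test needs one pair of occasions. The analysis sentence names exactly two, both after the intervention. A contrast with no pre-intervention value cannot show that awareness rose. A lasting benefit would look like no effect, and a benefit that faded but remained above baseline would look like a loss.

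If the sentence is read as two tests, each follow-up against an unstated baseline, a second problem appears. Both tests then sit under the primary question at 0.05 with no order between them, although 6.1.3 names and sizes only the 12-month test. A positive one-month result with a negative 12-month result could be reported as a success for a study that was sized on 12-month awareness.

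This is more than detail left for a statistical analysis plan. The protocol states its primary comparison more than once, and the statements do not agree. The study has no control group, so the choice of paired contrast carries the whole primary inference.

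**Working it through.** **1. What the sized test is.** Inputs from 6.1.3: 250 pairs; discordant cells 1.0% (aware before only) and 5.0% (aware after only); concordant aware 4.0%; two-sided alpha 0.05.

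- Aware before: 4% + 1% = 5%. Aware at 12 months: 4% + 5% = 9%.
- Expected discordant pairs: 250 × 0.06 = 15, of which a share 5/6 favour the later time.
- Arcsine approximation: Φ(|2·asin√(5/6) − 2·asin√0.5| × √15 − 1.96) = Φ((2.3005 − 1.5708) × 3.873 − 1.96) = Φ(0.866) = 0.807.

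This reproduces the stated 80.7%. Exact McNemar with the same inputs gives about 69%. Either figure belongs only to before versus 12 months. The protocol gives no discordance rates for one month versus 12 months, so the power of the sentence in 6.1.5.1, taken literally, is undefined.

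**2. Literal reading: one month versus 12 months.** Exact two-sided McNemar, 250 pairs, summed over the multinomial distribution of the discordant cells. All cell values are assumptions.

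| Aware at 1 month only / at 12 months only | Situation | P(significant) |
|---|---|---|
| 1% / 1% | effect maintained | 0.9% in total |
| 3% / 3% | effect maintained | 2.7% in total |
| 10% / 10% | effect maintained | 3.7% in total |
| 5% / 3% | 2-point fall | 14%, as a decline |
| 7% / 4% | 3-point fall | 23%, as a decline |
| 5% / 1% | 4-point fall | 69%, as a decline |
| 25% / 10% | 15-point fall | 98.0%, as a decline |
| 20% / 5% | 15-point fall | over 99%, as a decline |

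None of these results depends on the baseline level, so none bears on whether the intervention raised awareness.

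**3. Reading in line with 6.1.2: two tests against baseline.** Suppose each test is at two-sided 0.05 and either could support success. The family-wise error is 1 − P(|Z₁| < 1.96 and |Z₂| < 1.96) for bivariate normal statistics with correlation ρ:

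- ρ = 0: 1 − 0.95² = 9.75%
- ρ = 0.5: 9.1%
- ρ = 0.7: 8.3%

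The two tests share the baseline measure, so some positive correlation is expected. The protocol does not give its value.

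**4. Which reading the text supports.**

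| Section | Contrast | Number of tests |
|---|---|---|
| 6.1.2 | before v after, short and long term | two |
| 6.1.3 | before v 12 months | one |
| 6.1.5.1 | 1 month and 12 months, baseline not named | one (literal) or two |

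Sections 6.1.2 and 6.1.3 agree that baseline is the comparator. They do not agree on whether one or two tests answer the primary question.

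**The case against.** The strongest reply is that this is a drafting slip with a clear intention. Section 6.1.3 is operative text: it states the hypothesis, the test and the alpha for the primary question. Section 6.1.2 speaks of before and after in the short and long term, which maps onto one month and twelve months. The heading of 6.1.5.1 asks about an increase. Nowhere does the protocol express an interest in decay. All three measures are collected and linked by identifier, so the intended comparison stays available. Section 6.1.3 also supplies a hierarchy of a kind, because it sizes only the 12-month test, and no section says that one-month success alone would answer the question.

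Most of this stands. A reader might infer that the study is planned to measure decay rather than effect. The documents do not support that; it is the least likely intention.

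A reader might also take the 39% at one month and the 24% at one year in section 5 and conclude that the literal test would almost certainly report a decline. That does not follow. The 24% comes from the randomised trial and the 39% from preliminary findings of a later implementation in breast screening services. Their difference is not a within-person fall, and a probability of 98% or more rests entirely on assuming a 15-point fall.

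What the reply does not remove is the inconsistency. The one sentence that specifies the primary analysis omits the comparator, and the two sections that supply it disagree on the number of tests.

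**Conclusion.** The point holds as an inconsistency between 6.1.5.1 and 6.1.3, and the analysis sentence is wrong as written. Followed literally, it cannot answer the primary question: the chance of significance runs from about 1% when the effect is maintained to over 98% (as a decline) for a 15-point fall. Those figures rest on 250 pairs, exact McNemar and assumed discordance rates that the protocol does not give. They illustrate the problem and do not forecast the result.

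Under the likelier reading, two unranked comparisons with baseline, the family-wise error is about 8.3% to 9.75% for correlations from 0.7 to 0. This assumes a normal approximation and that either result could be claimed as success. The protocol does not say that either could, but 6.1.5.1 does not exclude it.

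The stated hypothesis, alpha and sample size are not affected by this point.

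**What to change.** Reword 6.1.5.1 along these lines: *Primary: McNemar test of baseline versus 12 months, two-sided alpha 0.05. Secondary: McNemar test of baseline versus one month, which does not determine the primary conclusion.* If a one-month versus 12-month comparison is wanted, label it descriptive.

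The cost is two sentences of protocol text. The sample size, the measurement schedule and the hypothesis in 6.1.3 stay as they are. In the same edit, reconcile the timing of the first follow-up: 6.1.3 describes a post-intervention questionnaire completed straight after the appointment, whereas 6.1.2 and 6.1.5.1 place it at one month.

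### The logistic model for factors tied to a successful PEP intervention ignores baseline awareness, so women already aware beforehand count as successes

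*Protocol*

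**What the plan says.** Protocol section 6.1.1 poses the secondary question: "Which, if any, demographic factors are associated with successful PEP intervention in primary care settings". Section 6.1.5.2 answers it with one model: "A logistic regression model will be built using the binary Breast Cancer Awareness Measure outcomes as the outcome variable". The predictors it names are the demographic factors collected. Section 6.1.2 lists eight of these, and baseline awareness is not among them. Section 6.1.5.1 uses the measure to sort women into two categories, aware and not aware, and section 6.1.5.2 gives no other coding and no time point.

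Elsewhere the protocol thinks in terms of change. The primary hypothesis compares before with 12 months after: "This will be tested by the McNemar test for paired proportions". Of the pairs aware at both times, section 6.1.3 says: "both cases will be classified as aware. These cases contribute no information to the hypothesis test". Section 6.1.2 picks women for telephone interviews about why PEP did not work by how little their awareness rose. The eligibility criteria in section 6.1.4.1 do not exclude women who are already aware.

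**The concern.** An intervention to raise awareness succeeds in a woman when she was not aware and becomes aware. A model of the aware state on demographic factors alone answers a different question: which women are aware afterwards, for whatever reason and since whenever. Any factor associated with awareness before PEP carries that association into the follow-up state, and would then be read as marking the women in whom PEP works.

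The definitions also pull apart. A woman aware at both times is a success in the regression. If her score hardly moved, she could also be invited to interview as someone in whom PEP did not succeed. What is at stake is the guidance on whom PEP suits in general practice. The primary comparison is not affected.

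**Working it through.** **Inputs.** Section 6.1.3 gives 250 women at 12 months and four cells: "in 90.0% of pairs, both cases will be classified as not aware and in another 4.0" per cent aware at both times; "1.0% of all pairs will show an outcome of aware for the before case only"; "5.0% of all pairs will show an outcome of aware for the after case only". Section 5 gives 24% aware at one year with PEP against 4% under usual care, and 3% rising to 39% over one month in the screening-service implementation. Section 6.1.2 gives eight demographic items.

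**Step 1: are the cells read correctly?** Expected discordant pairs are 250 × (0.01 + 0.05) = 15, of which 5/6 favour PEP. With the arcsine approximation and two-sided alpha 0.05, power = Φ{√15 × [2 arcsin √(5/6) − 2 arcsin √(1/2)] − 1.96} = Φ(3.873 × 0.730 − 1.96) = Φ(0.866) = 80.7%. This is the protocol's figure. The match only confirms the inputs; the choice of power method plays no part in this point.

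**Step 2: who counts as a success on the planning figures?**
- Aware at baseline: 4.0% + 1.0% = 5.0%, or 12.5 of 250.
- Aware at 12 months: 4.0% + 5.0% = 9.0%, or 22.5 of 250.
- Of those, aware beforehand: 4.0/9.0 = 44.4%, or 10 of 22.5.
- Newly aware: 5.0/9.0 = 55.6%, or 12.5 of 22.5.

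**Step 3: larger effects.** If every woman aware at baseline stays aware, the share is baseline awareness divided by follow-up awareness. That is an upper bound.
- One year: 4/24 = 16.7%. This takes the usual-care 4% as the baseline, which is an assumption.
- One month: 3/39 = 7.7%.

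**Step 4: from share to distortion.** The share of already-aware women is not itself a bias, so an illustration is needed. The group splits here are assumed. Take a factor that divides women 50/50 and has no effect on becoming aware.
- *Planning figures.* Let baseline awareness be 7.5% and 2.5% in the two groups (mean 5%). With persistence 4/5 and conversion 5/95, follow-up awareness is 0.075 × 0.8 + 0.925 × 0.0526 = 10.9%, against 0.025 × 0.8 + 0.975 × 0.0526 = 7.1%. The odds ratio is (0.109/0.891)/(0.071/0.929) ≈ 1.6.
- *24% aware at follow-up.* Let baseline awareness be 6% and 2% (mean 4%), with all persisting and conversion 20/96. Follow-up awareness is 25.6% against 22.4%, an odds ratio of about 1.2.

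In both cases the true odds ratio for becoming aware is 1.0. Conditioning on baseline awareness, by covariate or by restriction, recovers it.

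**Step 5: what restriction leaves.** Women not aware at baseline: 250 − 12.5 = 237.5. Events: 12.5 (5.3%). Over eight items that is 12.5/8 ≈ 1.6 events per item, against 22.5/8 ≈ 2.8 for the model as written.

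**The case against.** The strongest reply is that section 6.1.5.2 is a sketch. It speaks of outcomes in the plural, names no time point, does not say that the demographic factors are the only terms, and sits under a question about success, which section 6.1.2 treats as change. Section 6.1.6 links all three awareness measures for each woman, so a baseline term fits the data, and an analysis plan not shown here could add one. This stands in part: nothing in the protocol forbids the right model. But the protocol does name an outcome and a set of predictors, and that model does not answer its own question.

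Four stronger readings do not stand.
- A reader might take 44% as a forecast. Section 6.1.3 presents its cells as the least effect worth detecting, and the results cited in section 5 imply much smaller shares.
- A reader might argue that, because McNemar's test sets aside women aware at both times, the regression must too. The test equally sets aside the 90% never aware, whom any regression of success must keep. The case rests on the meaning of success, not on what McNemar's test drops.
- A reader might name education as a factor that will mislead. Section 3 links less education to delay in presenting, not to prior awareness. The documents show no size of distortion for any particular factor.
- A reader might expect the corrected model to show for whom PEP works. The design is before-after without a control group, so it can show only who became aware.

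**Conclusion.** The point holds as a mismatch between a secondary question and its stated model. The mismatch is present at any effect size; its weight depends on the effect. Already-aware women make up 44% of those aware at 12 months under the minimum-effect planning cells, at most about 17% if one-year awareness reaches 24% from an assumed 4% baseline, and at most 8% at one month if awareness rises from 3% to 39%. The odds ratios of 1.6 and 1.2 are illustrations on assumed group splits, not estimates for any listed factor. All of this takes section 6.1.5.2 at its word, with awareness at follow-up as the outcome and demographic predictors alone. The correction is worth making before analysis, but it concerns a secondary question only.

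**What to change.** Amend section 6.1.5.2 to state that the outcome is awareness at a named follow-up time, and that the model either includes baseline awareness as a covariate or is fitted only in women classified as not aware at baseline. Baseline status is already collected and linked by the unique identifier, so the change is a sentence and needs no new data.

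The cost differs by option. Restriction answers the question most directly. It drops about 5% of women (12.5 of 250) but, on the planning figures, also 10 of the 22.5 events, leaving about 12.5. The covariate keeps every woman, adds one term, and assumes that each factor acts alike on staying aware and on becoming aware. Either way the number of demographic predictors should be limited in advance and the result labelled exploratory. The text should also say that, without a control group, the model describes who became aware and does not estimate a causal effect of PEP by subgroup.
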